5.2.1 Pseudotumor Cerebri

Pseudotumor cerebri (PTC) must be confirmed by proper history, exam and other clinically relevant studies. Symptoms/signs of PTC include headache, papilledema, visual field defects (ocular/visual), and absence of focal neurological symptoms, except for occasional cranial nerve (CN) VI palsy (neuropathy: cranial CN VI). Cerebrospinal fluid should be evaluated and should be negative for signs of infection. However, lumbar puncture should be avoided while active coagulopathy is present. An opening pressure should be obtained; a pressure > 200 mm water helps to establish the diagnosis of PTC. A CT or MRI of the brain (to evaluate for meningitis, intracranial bleed, intracranial thrombosis, etc.) should be performed and should be compatible with PTC. Neurological and ophthalmologic consultations should be obtained in order to assist in making the proper diagnosis. Carefully follow the visual field status of the patient. One should also strongly consider obtaining a MRI/MRV to exclude the possibility of a sagittal sinus thrombosis. Consider acetazolamide (Diamox) therapy and periodic lumbar puncture with therapeutic removal of cerebrospinal fluid as appropriate for age/size.

If PTC develops:

- Hold tretinoin until this toxicity improves to Grade 0 or 1 (“mild” headache).

- Restart tretinoin at 75% of the original dose (19 mg/m²/day divided twice daily). If PTC reoccurs, hold tretinoin as above and then resume at 50% of original dose (12.5 mg/m²/day divided twice daily).

If the patient tolerates reduced dosing for more than 7 days, dose re-escalation can be attempted. Dose escalation from 50% (12.5 mg/m²/day divided twice daily) to 75% (19 mg/m²/day divided twice daily) to 100% (25 mg/m²/day divided twice daily) at 7 day intervals may be attempted if clinically appropriate.

5.3 Arsenic Trioxide Dose Modifications

Missed doses due to holidays or dose modifications do not need to be made up. However, if more than 2 doses are missed in a 4 week period due to holidays (not dose modifications), then make-up doses (following Day 26 of Consolidation Cycles 1 - 4) may be administered at the discretion of the treating physician.

5.3.1 Hepatotoxicity

At initial diagnosis, patients may have abnormal liver function tests due to their malignancy and no dose adjustment of arsenic trioxide is needed at initiation of therapy. Hepatotoxicity that occurs during arsenic trioxide treatment should prompt dose modifications as noted below.

If during arsenic trioxide administration, the patient has either:

- AST > 5 fold increase over the upper limit of normal (ULN)
- or direct bilirubin > 2 mg/dL

then hold arsenic trioxide until AST ≤ 3x ULN and direct bilirubin ≤ 0.5 mg/dL, after which resume arsenic trioxide treatment with a 50% dose reduction (0.075 mg/kg/day) during the first 7 days.

After 7 days of the reduced dose, and in the absence of worsening of the previous toxicity, arsenic trioxide should be resumed at full dose.

If a patient meets hepatotoxicity criteria for holding arsenic trioxide a second time, again hold arsenic trioxide until AST ≤ 3x ULN and direct bilirubin ≤ 0.5 mg/dL, then resume treatment with a 50% dose reduction (0.075 mg/kg/day) for all further doses of arsenic trioxide (no re-escalation of dose). If hepatotoxicity recurs while on 50% dosing, hold arsenic trioxide again until AST ≤ 3x ULN and direct bilirubin ≤ 0.5 mg/dL prior to restarting again at the 50% dose reduction (0.075 mg/kg/day). Please notify the study chair of cases in which hepatotoxicity occurs while on 50% dosing.

5.3.2 Hematological Toxicity

During Induction: No dose adjustment is required for anemia, decreased neutrophil count or decreased platelet count.

During Consolidation: If the patient has absolute neutrophil count < 1,000/uL or platelets < 50,000/uL lasting more than 5 weeks, then during the next cycle arsenic

trioxide should be dosed at 75% (0.11 mg/kg/day). If the patient again has absolute neutrophil count < 1,000/uL or platelets < 50,000/uL lasting more than 5 weeks, then during the next cycle arsenic trioxide should be dosed at 50% (0.075 mg/kg/day).

5.3.3 Nausea/Vomiting

Nausea/vomiting of any grade should be handled with symptomatic treatment with anti-emetics. If > 6 - 8 episodes occur daily, despite adequate trial of anti-emetics, then hold treatment until clinical improvement before resuming treatment at full dose. If treatment-refractory nausea/vomiting recurs, then hold treatment until improvement to Grade \leq 1 and then resume treatment with a 50% dose reduction (0.075 mg/kg/dose). The dose may be escalated back to 100% (0.15 mg/kg/dose) at the next cycle.

When selecting anti-emetics, investigators should consider the potential for QTc prolongation when used in conjunction with arsenic trioxide.

5.3.4 Cardiac Toxicity

Guidelines for the management of prolongation of the corrected QT (QTc) interval are as follows:

Measure the QT interval (from the start of the Q wave to the end of the T wave) and the preceding RR interval. The QTc interval will be calculated using Bazett's formula: the QT interval (msec) divided by the square root of the RR interval (msec).

- QTc interval 450 - 500 msec: Continue arsenic. Serum K⁺, Mg⁺⁺, and Ca⁺⁺ should be monitored and repleted only if low.
- QTc interval 501 - 600 msec: Hold arsenic temporarily and replete serum K⁺, Mg⁺⁺, and Ca⁺⁺ with IV and/or oral supplements immediately. Serum K⁺ and Mg⁺⁺ should be repleted to minimum target levels of 4.0 and 1.8 mg/dL, respectively. Discontinue any medications that prolong the QT interval. Resume arsenic on same day if target levels are achieved; re-check serum electrolytes prior to the next dose.
- QTc interval > 600 msec: Hold arsenic. Aggressive IV K⁺ and Mg⁺⁺ repletion. If the QTc interval falls below 600 msec, outpatient management may be considered with additional oral supplements and an ECG should be repeated the following day and/or prior to further arsenic treatment. Serum K⁺ and Mg⁺⁺ should be repleted to minimum target levels of 4.0 and 1.8 mg/dL, respectively. Discontinue any medications that prolong the QT interval. Resume arsenic on same day if target levels are achieved; re-check serum electrolytes prior to the next dose. If the QTc interval does not fall below 600 msec with this level of repletion, the patient should undergo ECG monitoring by telemetry, preferably in the hospital, along with continued IV K⁺ and Mg⁺⁺.
- Consider cardiology consultation if QTc is found to be prolonged.
- If syncope or rapid or irregular heartbeat develops, the patient should be hospitalized for monitoring and serum electrolytes should be assessed. Treatment with arsenic trioxide should be temporarily discontinued until

the QTc interval regresses to below 450 msec, electrolyte abnormalities are corrected, and the syncope and irregular heartbeat cease.

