3.2.4.3 EKG Abnormalities

- Patients with a pre-existing diagnosis of a prolonged QT syndrome (even if QTc is normal at the time of APL diagnosis) are excluded due to the use of arsenic trioxide, which can prolong the QT interval.
- Patients with a baseline QTc of > 450 msec are excluded. Bazett's formula is to be used for measurement of the corrected QT interval: the QT interval (msec) divided by the square root of the RR interval (msec).
- Patients with a history or presence of significant ventricular or atrial tachyarrhythmia are excluded.

- Patients with right bundle branch block plus left anterior hemiblock, bifascicular block are excluded.

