4.1.3 Concomitant Therapy

An extensive number of medications have been reported to prolong the QTc interval that could potentially exacerbate the effect of ATO on the QTc interval. Caution should be taken when using any medications concomitantly with ATO. Since this list of medications can potentially change during the time this protocol is active, please refer to the following reference website for a current and complete list:

<https://www.crediblemeds.org/everyone/composite-list-all-qtdrugs/>

These medications should be avoided during ATO therapy if other options exist. If these agents are used, they should be discontinued in any patient with normal serum electrolytes, calcium and magnesium who is found to have a QTc > 500 msec. Forty-eight hours after discontinuation of the agent, if the QTc remains > 500 msec or the patient is unable to discontinue these medications, the ATO must be discontinued.

Azole antifungal medications may increase ATRA toxicity due to inhibition of cytochrome P-450 metabolism of ATRA, and thus toxicities (including pseudotumor cerebri and renal dysfunction) should be monitored closely during concomitant use.

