4.2.2 Required Observations in Induction – Standard Risk APL

All baseline studies must be performed prior to starting protocol therapy unless otherwise indicated below. Obtain other studies during Induction as indicated.

- | |
|---|
| 
 a. History b. Physical Exam with VS: weekly c. Ht, Wt, BSA: Days 1, 29 and 57 d. Performance status e. Pregnancy test: Female patients of childbearing potential require a negative pregnancy test prior to starting treatment; sexually active patients must use an acceptable method of birth control. f. CBC, differential, platelets: daily during Week 1, then at least once weekly g. Urinalysis h. Electrolytes including Ca⁺⁺, Mg⁺⁺, K⁺ and creatinine: daily during Week 1, then at least once weekly i. Uric Acid j. AST, ALT, Total Bilirubin (and Direct Bilirubin if Total Bilirubin is >2 mg/dL): Once weekly k. Cholesterol triglycerides l. PT, PTT, fibrinogen, D-Dimer: daily during Week 1, then on Days 8, 15 and 29 (more frequently if needed for active coagulopathy) m. ECG for QTc monitoring: Weekly n. Echocardiogram or MUGA o. BMA for morphology: At diagnosis and Day 29 and every 2 weeks thereafter as needed until hCR/hCRi p. BMA for flow cytometry, cytogenetics & FISH: At diagnosis q. BMA for clinical RQ-PCR of PML-RARα: At diagnosis. This clinical testing is separate from research samples submitted for the optional MRD study; this mandatory clinical testing is not free of charge (cost is not covered by the study), but the specimen must be sent to one of the approved labs for PML-RARα RQ-PCR testing; a list of approved labs is available on the protocol-specific web page of the COG website. r. FLT3 (optional)*: bone marrow (or peripheral blood if bone marrow is unavailable) at diagnosis. See Section 15.1 for details. s. Research MRD (optional)*: bone marrow and peripheral blood at diagnosis and Day 29 of Induction. See Section 15.2 for details. Results of this research testing will not be returned to sites. This research testing does not take the place of the mandatory RQ-PCR clinical testing that must be done at the time of initial diagnosis (see observation “q” above). t. Coagulopathy (optional)*: peripheral blood at diagnosis (if available), Day 1, Day 8, Day 15 and Day 29 of Induction. See Section 15.3 for details. |
|---|

*Only obtain in patients who have consented to participation in this component of the trial.

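### Sections 3.2.4.3 and 5.3.4 print Bazett's formula with RR in msec instead of seconds, so the printed QTc is 31.6 times too small for its own limits

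*Combined protocol and SAP*

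**What the plan says.** Section 3.2.4.3 sets the eligibility limit: "Patients with a baseline QTc of > 450 msec are excluded". It names Bazett's formula for the correction and defines it as "the QT interval (msec) divided by the square root of the RR interval (msec").

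Section 5.3.4 repeats that definition for dose modification during arsenic trioxide (ATO) treatment. It first tells sites what to measure: "Measure the QT interval (from the start of the Q wave to the end of the T wave) and the preceding RR interval". It then sets bands in msec. From 450 to 500, arsenic continues. The next band reads "QTc interval 501 - 600 msec: Hold arsenic temporarily and replete serum" potassium, magnesium and calcium. Above 600, arsenic is also held.

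Three further provisions bear on how the formula is used:

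- Section 3.2 states that the eligibility criteria are to be read literally, without waiver, and verified from source records at audit.
- Section 4.2.2 requires "ECG for QTc monitoring: Weekly" in Induction. Section 4.8.2 requires the same for high risk patients, and the Consolidation sections require weekly ECGs while ATO is given.
- Section 4.1.3 applies a 500 msec limit to patients on QT-prolonging drugs but gives no formula of its own.

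**The concern.** Bazett's correction divides QT by the square root of RR expressed in seconds. At an RR of one second the divisor is then 1 and QTc equals QT, so the result stays on the msec scale of the limits. If RR is entered in msec, the divisor at the same heart rate is 31.6, and the result falls far below every limit in the protocol.

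The formula decides whether a patient may enter the trial and whether a drug known to prolong QTc is held. Section 5.3.4 does not simply accept a machine reading. It tells sites to measure both intervals and states how QTc is to be calculated. A site that followed the text exactly would never exclude a patient on baseline QTc and never hold arsenic for a prolonged one.

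**Working it through.** **Inputs.** The formula and the limits of 450, 500 and 600 msec come from Sections 3.2.4.3 and 5.3.4. The documents give no example QT or RR values, so those below are assumptions for illustration. They cover RR from 500 to 1000 msec, which is 120 down to 60 beats per minute.

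**Step 1: size of the error.**

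- As printed: QT (msec) / sqrt(RR in msec).
- Bazett with RR in seconds: QT (msec) / sqrt(RR in msec / 1000).
- Ratio of the second to the first: sqrt(1000) = 31.6, whatever the QT and RR.

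**Step 2: examples.**

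| QT (msec) | RR (msec) | As printed | RR in seconds | Action under the protocol limits, RR in seconds |
|---|---|---|---|---|
| 400 | 800 | 400/sqrt(800) = 14.1 | 400/sqrt(0.8) = 447.2 | Not excluded |
| 550 | 1000 | 550/sqrt(1000) = 17.4 | 550/sqrt(1.0) = 550.0 | Temporary hold |
| 500 | 600 | 500/sqrt(600) = 20.4 | 500/sqrt(0.6) = 645.5 | Hold, above 600 |

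As printed, all three values fall far below 450, so none would lead to exclusion or a hold.

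**Step 3: QT needed to reach each limit.** For a limit L, the QT needed is L × sqrt(RR), with RR in the unit of the formula. The ranges run from RR 500 to RR 1000 msec.

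| Limit | QT needed as printed (msec) | QT needed with RR in seconds (msec) |
|---|---|---|
| 450 | 10,062 to 14,230 | 318 to 450 |
| 500 | 11,180 to 15,811 | 354 to 500 |
| 600 | 13,416 to 18,974 | 424 to 600 |

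The printed formula would need a QT interval of 10 seconds or more.

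**Step 4: ceiling.** Even if QT filled the whole RR interval, the printed formula would give RR/sqrt(RR) = sqrt(RR). That is 22.4 at RR 500 msec and 31.6 at RR 1000 msec, so no reading in this range comes near 450.

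**Step 5: is it corrected elsewhere?** No other section gives a formula or a conversion of RR to seconds. The unit is written in running text, identically, in two separate sections, so a fault in reading the PDF is unlikely.

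**The case against.** The strongest reply is that this is a one-word slip that reveals itself. The formula is correctly named, the limits are in msec, and anyone calculating by hand would get a value between about 13 and 20 against a limit of 450 and see that something was wrong. ECG machines and clinicians usually apply Bazett with RR in seconds. A constant factor of 31.6 cannot quietly move a borderline patient across a limit. All of this stands, and it is why the practical effect is likely small. It does not make the text right: the protocol asks for its eligibility criteria to be read literally, and read that way this criterion cannot operate.

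A reader might infer two stronger things.

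- **That ineligible patients were enrolled, or that arsenic was continued when it should have been held.** Nothing in the documents shows that any QTc was calculated as printed or that any patient was misclassified.
- **That Sections 4.1.3 and 5.3.4 conflict.** Section 5.3.4 says "Discontinue any medications that prolong the QT interval. Resume arsenic on same day if target levels are achieved". Section 4.1.3 says of QT-prolonging drugs that "they should be discontinued in any patient with normal serum electrolytes, calcium and magnesium who is found to have a QTc > 500 msec", and that 48 hours after the drug is stopped, "if the QTc remains > 500 msec or the patient is unable to discontinue these medications, the ATO must be discontinued". A reader might see permission to restart too early. However, 5.3.4 requires such drugs to be stopped before its same-day resumption applies, and 4.1.3 does not say that arsenic is held during the 48 hours. A site can resume under 5.3.4 and then discontinue if QTc is still above 500 msec at the 48-hour check. If the drug cannot be stopped, the mandatory rule in 4.1.3 applies directly. What remains is a missing cross-reference and a clinical preference about those 48 hours, which is not an error in the plan.

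**Conclusion.** The formula is wrong as written in both sections, by a constant factor of sqrt(1000) = 31.6. Calculated literally, the exclusion above 450 msec and the arsenic holds at 501-600 and above 600 msec could never trigger. The factor follows from the units alone; only the worked examples rest on assumed QT and RR values.

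The intended unit is evident from the context, so the likely effect on patients is small. No endpoint definition, sample size or power figure uses the formula. The correction is still worth making, because the error sits in an operative eligibility criterion and an operative safety rule, not in background text. The conclusion goes no further than the unit: it implies neither misclassified patients nor a contradiction between the concomitant-medication rule and the dose-modification rule.

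**What to change.** In Sections 3.2.4.3 and 5.3.4, change the unit attached to the RR interval from msec to seconds and leave QT in msec, so that QTc (msec) = QT (msec) / sqrt(RR (seconds)). The 450, 500 and 600 msec limits stay as they are. Because Section 5.3.4 asks sites to measure RR, a short worked example would help, such as QT 400 msec and RR 0.8 seconds giving 447 msec.

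The cost is one word in two places and a memo to sites. Design, sample size and analysis do not change.

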2.4 Cardiac Toxicity in APL Therapy

Many APL treatment regimens rely upon high cumulative doses of anthracyclines. It is well known that anthracycline exposure places patients at risk for significant cardiac toxicity.^{21,22} The risk increases with higher cumulative doses (especially over 300 mg/m²), and the risk is higher when children are exposed at a young age.²³ On the European APL93 and APL2000 trials a total of 26 children and 58 adolescents were treated. The treatment regimens included a total of 495 mg/m² of daunorubicin. Three children experienced significant cardiac toxicity, including one patient with fatal heart failure during Consolidation, one patient who developed heart failure 6 years after completion of therapy and was managed with medical therapy, and one patient who relapsed and received additional mitoxantrone and auto-transplant prior to developing heart failure requiring a heart transplant.²⁴ On the AML intergroup C9710 trial, there were 2 deaths attributed to cardiac toxicity among 56 children (personal communication, [name]).

A goal of AAML1331 is to further improve long-term outcomes and quality of life for survivors of childhood APL. For standard risk patients, no anthracyclines will be used in their treatment. For high risk patients, the cumulative dose of anthracycline will be reduced to 48 mg/m² of idarubicin (approximately 192 mg/m² daunorubicin equivalents). The current study will include repeated cycles of ATO, which is known to prolong the QTc during treatment. On the recently closed AAML0631, children received ten weeks of ATO (given as two courses of five weeks each) and QTc prolongation was monitored closely on the trial. Twenty four patients had prolonged QTc during their ATO cycles, but all were Grade 1 or 2, transient, and did not require dose adjustment.⁷

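### Section 5.3.4 gives the potassium target for restarting arsenic in mg/dL; as printed it equals 1.02 mmol/L and would never hold up a restart

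*Combined protocol and SAP*

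**What the plan says.** Section 5.3.4 of the combined protocol and SAP sets out what to do with arsenic trioxide as QTc lengthens. Two bullets suspend the drug: "QTc interval 501 - 600 msec: Hold arsenic temporarily and replete serum" potassium, magnesium and calcium, and "QTc interval > 600 msec: Hold arsenic". Both bullets say that potassium and magnesium "should be repleted to minimum target levels of 4.0 and 1.8 mg/dL, respectively". Both then give the restart rule: "Resume arsenic on same day if target levels are achieved; re-check serum electrolytes prior to the next dose".

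The word *respectively* assigns 4.0 to potassium and 1.8 to magnesium. The only unit printed is mg/dL. Calcium is to be repleted in the 501-600 msec bullet but has no numerical target.

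A separate bullet covers syncope or a rapid or irregular heartbeat. There arsenic stays off until "the QTc interval regresses to below 450 msec, electrolyte abnormalities are corrected, and the syncope and irregular heartbeat cease".

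**The concern.** Milligrams per decilitre is a sensible unit for the magnesium figure but not for the potassium figure. Potassium at 4.0 mg/dL is far below any plausible serum value, so, read literally, the potassium half of the restart condition is met by every patient.

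The sentence matters because it is a decision rule. Reaching the targets is what permits arsenic to resume on the day QTc was found above 500 msec. The 501-600 msec bullet asks for no QTc value and no repeat ECG before that restart, unlike the syncope bullet. On a literal reading, magnesium 1.8 mg/dL is then the only printed number that still controls a restart in that range.

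**Working it through.** **Inputs.** From Section 5.3.4: potassium 4.0 and magnesium 1.8, with mg/dL as the one printed unit. The documents do not give atomic masses, so I use the physical constants: potassium 39.1 and magnesium 24.3. Potassium is monovalent, so 1 mEq/L = 1 mmol/L.

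**Formula.** mmol/L = (mg/dL x 10) / atomic mass; in reverse, mg/dL = mmol/L x atomic mass / 10. The plan derives no figure here, so there is nothing to reproduce; the check is a unit conversion.

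**Targets.**
- Potassium as printed: 4.0 x 10 / 39.1 = 1.02 mmol/L.
- Magnesium as printed: 1.8 x 10 / 24.3 = 0.74 mmol/L, a plausible target.
- Potassium if 4.0 mEq/L was meant: 4.0 x 39.1 / 10 = 15.6 mg/dL.
- Printed against inferred potassium target: 1.02 / 4.0 = 0.26, or 26%.

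**What the printed target lets through.** The patient values below are assumed, for illustration.

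| Potassium, mmol/L | In mg/dL (x 39.1 / 10) | Meets 4.0 mg/dL? | Meets 4.0 mEq/L? |
|---|---|---|---|
| 2.0 | 7.8 | yes | no |
| 2.5 | 9.8 | yes | no |
| 3.0 | 11.7 | yes | no |
| 3.5 | 13.7 | yes | no |

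Any potassium of about 1.02 mmol/L or more meets the printed target.

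**Whether another section corrects it.**
- The required-observation lists (for example Sections 4.2.2, 4.3.2 and 4.8.2) name potassium without a unit or a threshold.
- Section 4.1.3 refers to normal electrolytes without numbers. Its stopping rule is "if the QTc remains > 500 msec or the patient is unable to discontinue these medications, the ATO must be discontinued", judged 48 hours after a QT-prolonging medicine is withdrawn. It covers only patients taking such a medicine and sets no potassium level.
- The electrolyte re-check before the next dose in Section 5.3.4 has no threshold of its own.

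Nothing in the documents supplies a correct potassium target.

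**The case against.** The strongest reply is that the number is right and only its label is wrong. Assuming the laboratory reports potassium in mmol/L or mEq/L, a clinician with a result of 3.0 would compare it with 4.0, see that it falls short and give more potassium, which is the right action. Harm requires converting the result to mg/dL first, and nobody is told to do that. The section's own logic also argues against the literal reading: potassium is replaced only if low at 450-500 msec, immediately at 501-600 msec and aggressively above 600 msec. A target of 1.02 mmol/L would make the higher tiers weaker than the lowest.

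Safeguards also remain: the repletion orders, the magnesium target, withdrawal of QT-prolonging drugs, the re-check before the next dose, consideration of a cardiology consultation, weekly ECGs and electrolytes during arsenic (daily electrolytes in the first week of Induction), and repeat ECG or telemetry above 600 msec. Few patients should reach the rule. Section 2.4 reports 24 patients with prolonged QTc in AAML0631, of whom "all were Grade 1 or 2, transient, and did not require dose adjustment".

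Much of this stands. It makes a misprint the likely explanation and limits the practical effect. It is also fair that no derived figure has been miscalculated, and that the missing calcium target and the lack of a repeat ECG at 501-600 msec are separate design questions, which changing the unit would not settle. What does not stand is that no correction is needed: a restart criterion for a QT-prolonging drug should not depend on each reader replacing the printed unit. The reassurance from AAML0631 is also partial, because patients there had ten weeks of arsenic (Section 2.4), against at least 20 weeks here (Section 2.10.4).

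**Conclusion.** The concern holds. Both bullets give potassium a unit that turns its target into 1.02 mmol/L, 26% of the value probably intended, and both make that target part of the condition for restarting arsenic the same day. No other section corrects it.

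The conclusion rests on two assumptions. The first is that a treated patient's potassium stays above about 1 mmol/L, which is what makes the printed condition always met; the documents give no range. The second is that mEq/L (mmol/L) was intended, which the documents do not state.

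The effect is limited to patients with QTc above 500 msec and is reduced by the remaining safeguards and by the natural reading of 4.0. The documents do not allow a count of affected restarts. The text should be corrected because it is an operative safety threshold. The EFS endpoint, the non-inferiority margins and the power calculations are untouched.

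**What to change.** In the 501-600 msec and above-600 msec bullets of Section 5.3.4, give each ion its own unit, for example: K+ 4.0 mEq/L (mmol/L) and Mg++ 1.8 mg/dL. The study chair should confirm the potassium unit before the text is issued.

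The cost is two edited sentences in an amendment, with no change to data collection, sample size or analysis.
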